 - > 15 hours prior to randomization or unknown time of last dose, only if 1) the local anti-fXa activity > 100 ng/mL for direct fXa inhibitors (apixaban, rivaroxaban or edoxaban), as per standard of care, and 2) the local anti-fXa activity level is obtained within 2 hours prior to consent. Note: Patients enrolled in this manner should receive a high andexanet dosing regimen.

- 6. Time from bleeding symptom onset ≤ 6 hours prior to the baseline imaging scan. Time of trauma (if applicable) or time last seen normal may be used as surrogates for time of symptom onset. (If the baseline scan is repeated to meet Inclusion Criterion #4, the time from bleeding symptom onset must be ≤ 6 hours prior to the repeat baseline imaging scan.)
- 7. Female patients of childbearing potential and male patients with female partners of childbearing potential must follow protocol-specified guidance for avoiding pregnancy for 30 days after the last dose of study drug.
- 8. Have a negative pregnancy test documented prior to enrollment (for females of childbearing potential).
- 9. NIHSS score \leq 35 at the time of consent.

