4.2. Exclusion Criteria

If a patient meets any of the following criteria, he or she is *not* eligible to participate in this trial:

- 1. Planned surgery, including Burr holes for hematoma drainage, within 12 hours after randomization. Minimally invasive surgery/procedures not directly related to the treatment of intracranial bleeding and that are not expected to significantly affect hematoma volume are allowed (e.g., Burr holes for intracranial pressure monitoring, endoscopy, bronchoscopy, central lines—Section 7.2, Section 7.3 and Appendix G).
- 2. GCS score < 7 at the time of consent. If a patient is intubated and/or sedated at the time of consent, they may be enrolled if it can be documented that they were intubated/sedated for non-neurologic reasons within 2 hours prior to consent.
- 3. *Purposefully left blank to align with the programmed database.*
- 4. Anticipation that the baseline and follow up brain scans will not be able to use the same imaging modalities (i.e., patients with a baseline CT scan should have a CT scan in follow up; similarly, for MRI).
- 5. Expected survival of less than 1 month (not related to the intracranial bleed).
- 6. Recent history (within 2 weeks) of a diagnosed TE or clinically relevant symptoms of the following:
 - Venous Thromboembolism (VTE: e.g., deep venous thrombosis, PE, cerebral venous thrombosis), myocardial infarction (MI), Disseminated Intravascular Coagulation (DIC), cerebral vascular accident, transient ischemic attack (TIA), acute coronary syndrome, or arterial systemic embolism (see Appendix H for DIC scoring algorithm).
- 7. Acute decompensated heart failure or cardiogenic shock at the time of randomization (see Appendix I for cardiogenic shock definition).

- 8. Severe sepsis or septic shock at the time of randomization (see Appendix I for sepsis definition).
- 9. The patient is a pregnant or lactating female.
- 10. Receipt of any of the following drugs or blood products within 7 days prior to consent:
 - a. VKA (e.g., warfarin).
 - b. Dabigatran.
 - c. PCC (e.g., KCentra[®]) or rfVIIa (e.g., NovoSeven[®]), or anti-inhibitor coagulant complex (e.g., FEIBA[®]), FFP, and whole blood.
- 11. Past use of andexanet (or planned use of commercial andexanet).
- 12. Treatment with an investigational drug < 30 days prior to consent.
- 13. Any tumor-related bleeding.
- 14. Known hypersensitivity to any component of andexanet.

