5.11.	Handling of Laboratory Samples Out of Stability	33
6. S	UPPORTING DOCUMENTATION	34
6.1.	Appendix 1: Technical Specifications for Derived Variables	34
6.2.	Appendix 2: Study and Participant Characteristics	44
6.2.1.	Protocol Deviations	44
6.2.2.	Demographics and Disease Characteristics	44
6.2.2.1.	Demographics and Disease Characteristics (Bleeding)	44
6.2.2.2.	Medical/Surgical History and Baseline Physical Examination	46
6.2.3.	Prior and Concomitant Medications	46
6.3.	Appendix 3: Instrument Scoring Details	46
6.3.1.	Glasgow Coma Scale	46

6.3.2.	Utility-Weighted mRS	46
6.3.3.	EQ-5D-5L Health State Index Score Calculations	47
6.4.	Appendix 4: Additional Details on Statistical Methods	
6.4.1.	COVID-19 Vaccine Risk Assessment	
6.4.1.1.	Vaccination	
6.4.1.2.	Potential Risks and Mitigation Measures	
6.4.1.3.	Reason for Not Collecting COVID-19 Information	
6.5.	Appendix 5: Changes to Protocol-Planned Analyses	
6.6.	Appendix 6: List of Abbreviations	
7.	REFERENCES	

LIST OF TABLES

Table 1:	Objectives and Endpoints	8
Table 2:	Analyses Sets	.15
Table 3:	Attributes of Primary (Composite) Estimand	.18
Table 4:	AEs and SAEs	.27
Table 5:	Clinically Significant Laboratory Criteria	.43
Table 6:	Clinically Significant Vital Sign Criteria	.43
Table 7:	EQ-5D-5L US cTTO Value Set	.47

VERSION HISTORY

This statistical analysis plan (SAP) for Study 18-513 is based on Protocol Version 3.0, dated 05 Dec 2022.

SAP Version	Version Date	Change	Rationale
0.2	07 Jun 2022	Not applicable	Original version
1.0	30 Nov 2022	 Updated primary efficacy analysis to using one stratification factor Updated sensitivity analyses for the primary endpoint Updated the analysis for secondary endpoint Updated analyses for correlation between effective hemostasis and anti-fXa activity Updated subgroup analysis Updated language in the section for interim analysis for better clarification Updated definition for the per protocol set 	Changes are made to align with the Protocol Amendment V3 and to incorporate comments from regulatory agency review
1.1	17 Apr 2023	 Added clarification of two data cutoff (DCO) points Added definition of screened set 	Changes are made to clarify the data used for the interim analysis, and the final analysis; and to differentiate the screened participants from the enrolled participants.

APPROVAL SIGNATURES

		20-Apr-2023 11:02 EDT
	, Alexion	Date dd Mmm yyyy
		20-Apr-2023 10:53 EDT
	, Alexion	Date dd Mmm yyyy
		21-apr-2023 12:43 IST
AstraZeneca	, ,	Date dd Mmm yyyy

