1.2. Study Design

This is a Phase 4, randomized, multicenter clinical study designed to determine the efficacy and safety of andexanet compared to usual care (UC) in participants presenting with acute ICrH (including intracerebral hemorrhage) within 6 hours of symptom onset (from the baseline imaging scan) and within 15 hours of taking an oral FXa inhibitor (from randomization). It should be noted that Protocol Amendment (PA) V1 modified Inclusion Criterion No. 3 to limit enrollment to participants with intracerebral hemorrhage to increase the homogeneity of the study population and to clarify eligible hematoma blood volume; consequently, there may be some nonintracerebral participants enrolled.

A summary of the study design can be found as below:

- The study will use a prospective, randomized, open-label design.
- Participants will be randomized 1:1 to receive either and exanet or UC stratified as follows, as detailed in PA V1:
 - Intended PCC use (yes versus no).
 - Time from symptom onset to the baseline imaging scan (< 180 minutes versus \geq 180 minutes).
- Randomization must occur within 15 hours following the last dose of the FXa inhibitor. For participants enrolled > 15 hours or where the last dose time of the FXa inhibitor is unknown, if a local anti-fXa activity level obtained within 2 hours after informed consent (as part of UC) and prior to randomization is > 100 ng/mL for direct FXa inhibitors (apixaban, rivaroxaban, and edoxaban), the participant may be enrolled, irrespective of the time of the last dose, and the participant will receive the high andexanet dosing regimen.
- UC will consist of any treatments (including no treatment) other than and exanet administered within 3 hours post-randomization that the Investigator and/or other treating physicians consider to be appropriate.
- For and example treatment, participants will receive 1 of 2 dosing regimens of and example based on which FXa inhibitor they receive and the amount and timing of the most recent dose, as indicated in Protocol Section 6.2. The and example and the gradient dosing regimens to be examined in this study are as follows:

- Low dose: 400 mg intravenous (IV) bolus, followed by a continuous infusion of 480 mg at 4 mg/min for 120 minutes.
- High dose: 800 mg IV bolus, followed by a continuous infusion of 960 mg at 8 mg/min for 120 minutes.

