6.1. Appendix 1: Technical Specifications for Derived Variables

The following derived data will be calculated prior to the analysis:

Defining the Per Protocol Set

The Per-Protocol Set (PPS) will include all participants in the ITT Set who did not have important protocol deviations impacting the primary hemostatic efficacy endpoint.

The reasons for exclusions and inclusion from the PPS will include the following subset of major protocol deviations:

- Inclusion/Exclusion:
 - Participant failed the following inclusion/exclusion:
 - Inclusion Criterion #3: An acute intracerebral bleeding episode of specified volume requirements
 - Even if the locally determined intracerebral bleed volume is out of per-protocol requirement, if subsequent average core lab screening volume assessment is within per-protocol requirements, then participant is eligible for PP set.
 - Inclusion Criterion #4: Performance of a head CT or MRI scan demonstrating the intracerebral bleeding within 2 hours prior to randomization
 - If CT/MRI scan is performed out-of-window/missing: If the EAC can determine an efficacy outcome, then participant is considered in PP set.
 - Inclusion Criterion #5: Specific treatment regimens and associated anti-fXa testing requirements with an FXa inhibitor
 - If central lab baseline/screening value collected within 2 hours of randomization or pre-treatment administration is >100ng/ml then participant is included into PP set
 - Inclusion Criterion #6: Where such timing is collected, time from bleeding symptom onset prior to the baseline imaging scan.
 - Inclusion Criterion #9: NIHSS score ≤ 35 at the time of consent (Protocol Amendment #2 only)
 - If NIHSS is performed out-of-window/missing: If the EAC can determine an efficacy outcome, then participant is considered in PP set.
 - Exclusion Criterion #1: Planned surgery affecting hematoma volume within 12 hours after randomization

- Exclusion Criterion #2: GCS score < 7 at the time of consent unless intubated and/or sedated for non-neurologic reasons <2 hours of consent
 - If GCS performed at informed consent is missing, then participant is excluded from PP set
 - Lack of evidence for intubation/sedation for non-neurological reason, then participant is excluded from PP set
 - If GCS is out-of-window; so long as the GCS documented is pre-treatment administration and >7, participant may be included into PP set.

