- Exclusion Criterion #10 (PA #2) or #11 (PA #1, Original protocol): Receipt of restricted drugs or blood products within 7 days prior to consent
- Exclusion Criterion #11 (PA #2) or #12 (PA #1, Original protocol):
 Past use of andexanet (or planned use of commercial andexanet)
- Exclusion #13 (Original protocol, PA#1) or #12 (PA #2): Treatment of investigational drug <30 days prior to consent
- Exclusion Criterion #16: NIHSS Score >35 at time of consent (PA #1 only)
 - See appliable exceptions in section above 'Inclusion Criterion #9: NIHSS score ≤ 35 at the time of consent (Protocol Amendment #2 only)'
- Randomization:
 - The wrong study treatment is assigned post-randomization:
 - Use of pro-coagulant blood products or haemostatic agent for participant randomized to and exanet <3 hours post randomization where and exanet is not administered within 3 hours post randomization.
 - Use of and examet for participant randomized to usual care <12hrs post randomization
 - Study treatment is given prior to randomization
- Investigational Product (Andexanet) Administration:
 - Missing dose or Treatment administered incorrectly:
 - Wrong bolus dose
 - Low and examet bolus dose if < 360mg administered
 - High and exanet bolus dose if < 720mg administered
 - Wrong infusion dose
 - Low and exanet infusion dose if < 432mg administered

Page 35 of 52 Alexion Confidential

- High and exanet infusion dose if < 864mg administered
- Start of bolus is >30 minutes after randomization and either >2 hours of baseline imaging scan or >6 hours of symptom onset
- Start of infusion is >15 minutes after end of bolus
- There is a mismatch between recommended and examet dose regimen and actual dose administered such that:
 - Subject assigned high dose but receives low dose and examet is excluded from PP set
 - Subjects assigned low dose but receives high dose and exanet are eligible for PP set.
- Procedural:
 - 12hr NIHSS assessments performed by assessor unblinded to participant's treatment allocation
 - Unless the EAC is able to determine hemostatic efficacy for affected participants, the following will render the participant not evaluable for the Per Protocol Set if EAC concludes the participant is 'Nonevaluable due to administrative reasons'.
 - NIHSS:
 - Missing NIHSS score at baseline and/or 12 hours postrandomization
 - Baseline NIHSS score is >2 hours prior to randomization or post-randomization
 - 12 hour NIHSS score is <11 hours or >13 hours postrandomization

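### Two per-protocol rules in SAP 6.1 do not match the protocol: no NIHSS check covers Amendment 3, and an out-of-window GCS of exactly 7 is not re-admitted

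*SAP*

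**What the plan says.** Protocol 10.4.2 leaves the full per-protocol definition to the SAP, and SAP Table 2 refers to Section 6.1. The wording there therefore decides who is in the set. SAP 5.3.3 uses the set once, for sensitivity analysis 2 of the primary endpoint.

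- **NIHSS.** One rule is "Inclusion Criterion #9: NIHSS score ≤ 35 at the time of consent (Protocol Amendment #2 only"). A second applies the same limit as Exclusion 16 and is tagged to Amendment 1 alone. The SAP version history says the plan is "based on Protocol Version 3.0, dated 05 Dec 2022", and Protocol 4.1 still carries Criterion 9 (NIHSS no higher than 35).
- **GCS.** Protocol 4.2 excludes "GCS score < 7 at the time of consent", and the SAP's main check uses the same limit. For a score taken out of window, the SAP says "so long as the GCS documented is pre-treatment administration and >7, participant may be included into PP set".
- **Late bolus.** Under product administration, the SAP removes an andexanet patient if "Start of bolus is >30 minutes after randomization and either >2 hours of baseline imaging scan or >6 hours of symptom onset". The protocol's own 6-hour limit is "Time from bleeding symptom onset ≤ 6 hours prior to the baseline imaging scan". Protocol 6.2 asks for dosing within 30 minutes of randomization and prefers it within 2 hours of the scan.
- **Local anti-fXa sample.** SAP 1.2 places it "within 2 hours after informed consent (as part of UC) and prior to randomization". Criterion 5 in Protocol 4.1 places it in the 2 hours before consent.

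**The concern.** A per-protocol analysis is useful only if its membership rules reproduce the protocol criteria they claim to enforce. Here one rule stops short of the current amendment, and another uses a cut-off one point away from the protocol's. Read literally, the first keeps a patient who fails a current entry criterion, and the second fails to bring back a patient who meets one. The version history records that the PPS definition was updated and that the changes were meant to align with Amendment 3, so a reader would expect both to be right. If the wording is settled only after unblinding, membership of the set becomes a post hoc decision.

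**Working it through.** No stated figure in the plan bears on this, so the check sets each rule beside its criterion.

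**1. NIHSS limit by protocol version**

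| Version | Limit in protocol | SAP 6.1 check |
|---|---|---|
| Original | none (the amendment log lists it as added in Amendment 1) | none needed |
| Amendment 1 | above 35 excluded (Exclusion 16) | yes |
| Amendment 2 | 35 or below required (Criterion 9) | yes |
| Amendment 3 | 35 or below required (Criterion 9) | none as worded |

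The gap is Amendment 3 alone. It matters for the endpoint. The item maxima in Protocol Appendix E sum to 3+2+2+2+3+3+8+8+2+2+3+2+2 = 42 (arms and legs scored on both sides). A patient entering at 36 can worsen by at most 42 − 36 = 6 points and so cannot meet the +7 failure criterion.

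**2. GCS 3 to 15, protocol rule against the out-of-window exception**

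- Scores 3 to 6: ineligible; not re-admitted. Agree.
- Score 7: eligible (7 is not below 7); not re-admitted (7 is not above 7). Disagree.
- Scores 8 to 15: eligible; re-admitted. Agree.

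The mismatch is one value, and only for scores out of window.

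**3. Local anti-fXa sample**

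With consent at time 0, Criterion 5 needs a sample between −2 h and 0, and SAP 1.2 describes one between 0 and +2 h. The intervals do not overlap, so the same sample cannot satisfy both. This concerns only patients whose last dose was more than 15 hours ago or at an unknown time.

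**4. Late-bolus rule**

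The rule removes a patient if randomization-to-bolus exceeds 0.5 h AND (scan-to-bolus exceeds 2 h OR onset-to-bolus exceeds 6 h). It was enumerated on a 15-minute grid of eligible times: onset to scan 0 to 6 h (25 values), scan to randomization 0 to 2 h (9 values), randomization to bolus 0 to 1.5 h (7 values).

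- Bolus within 30 minutes: 25 × 9 × 3 = 675 cells, of which 135 have onset-to-bolus above 6 h. Removed: 0. A fully adherent patient can reach 6 + 2 + 0.5 = 8.5 h and stays.
- Bolus later than 30 minutes: 25 × 9 × 4 = 900 cells. Removed: 560, of which 110 by the 6-hour limb alone.

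These counts show the logic and are not patient frequencies. An example of the last group: scan at 5 h 00 after onset, randomized at 6 h 00, bolus at 6 h 35. Scan to bolus is 1 h 35, so only the 6-hour limb removes this patient, who has already missed the 30-minute limit.

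**The case against.** The best defence is that the tags are shorthand not brought up to date, that the set is by its own terms built from a subset of major deviations, and that the primary analysis is on the ITT Set. SAP 5.2.1 also tabulates eligibility failures by arm and protocol version, so an Amendment 3 failure would be visible. All of this stands. Intent to skip Amendment 3 is not shown, and the consequence is small. It does not remove the need to correct the text, because the NIHSS tags are expressly restrictive and the GCS exception differs from the SAP's own main check.

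Four stronger readings are tempting, and the documents do not support them.

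- **That the 6-hour eligibility limit is misstated, or that the arms cease to be comparable.** SAP 6.1 enforces Criterion 6 from onset to scan, as the protocol does. The bolus limb sits in a dosing rule and bites only after the 30-minute limit has been missed. Any andexanet dosing rule acts on one arm, and usual care has its own 3-hour window. What remains is that the limb has no source in the protocol.
- **That the one-way core-lab rule keeps ineligible patients.** The SAP re-admits a patient with an out-of-range local volume "if subsequent average core lab screening volume assessment is within per-protocol requirements, then participant is eligible for PP set" and has no converse. Criterion 3 asks only for an estimated volume, so a patient in range locally met it. A two-way rule would be a preference.
- **That Exclusions 10 to 12 are switched off for Amendment 3.** Their tags lack any restrictive word and read as a key to changed numbering; Amendment 3 keeps the Amendment 2 numbers.
- **That the consent-timing conflict makes the PPS misapply Criterion 5.** SAP 1.2 is a design summary. The PPS rule cites Criterion 5 itself and re-admits on a central-lab value above 100 ng/mL.

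**Conclusion.** The point holds for two rules. As worded, the PPS has no NIHSS check for Amendment 3 patients, and its out-of-window GCS exception leaves out the eligible score of 7. Two further places need reconciling: SAP 1.2 against Criterion 5, and the onset-to-bolus limb against Protocol 4.1 and 6.2. The second touches only andexanet patients already dosed more than 30 minutes after randomization.

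The effect is confined to sensitivity analysis 2. The documents give no enrolment by amendment, no number with NIHSS above 35 and no number with an out-of-window GCS of 7, so the number affected cannot be derived and could be zero. The conclusion rests on a literal reading of the version tags, and on the amendment log for the absence of an NIHSS limit in the original protocol.

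**What to change.** In SAP 6.1:

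1. Tag the Criterion 9 check as Amendment 2 onward. For clarity, extend the version key on Exclusions 10 to 12 to Amendment 3.
2. In the out-of-window GCS exception, replace above 7 with 7 or above.
3. Reconcile the 6-hour onset-to-bolus limb with Protocol 4.1 (Criterion 6) and 6.2, or state its rationale.

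Also reconcile SAP 1.2 with Criterion 5 on the timing of the local anti-fXa sample relative to consent.

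The cost is a few one-line edits before unblinding, using data already collected. Item 1 can only shrink the PPS and item 2 can only enlarge it, probably by very few patients. No change to the primary analysis, sample size or alpha is needed.

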4.4. Criteria for Discontinuation of Andexanet

And exampt may be prematurely discontinued for a number of reasons, including:

• Any intolerable AE that cannot be ameliorated by appropriate medical intervention or that in the opinion of the Medical Monitor or Investigator would lead to undue risk if the patient were to continue on treatment.

Patients who discontinue study drug should still continue in the study. Patients who discontinue the study after receiving any amount of andexanet should undergo all follow-up safety procedures.

Reasons for all discontinuations of andexanet will be recorded.

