7.5. Infusion Reactions

As discussed in the IB, mild to moderate infusion reactions were reported in healthy subjects who received and exanet and rarely occurred in bleeding patients who were treated in a Phase 3b/4 study. These infusion reactions have generally resolved without interruption of the infusion or medical intervention. In the event that the Investigator determines that intervention is

warranted, consideration may be given to slowing the infusion rate, or temporary interruption of the dose followed by re-starting the infusion at a slower infusion rate. Treatment with diphenhydramine may also be considered.

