5.3.3. Sensitivity Analysis

The following sensitivity analysis will be performed to evaluate the robustness of the primary efficacy results:

Sensitivity analysis 1: The same analysis for the primary endpoint described in Section 5.3.2 with 2 stratified factors in the CMH test: intended PCC use (yes versus no) and the time from symptom onset to baseline imaging assessment (< 180 minutes versus \ge 180 minutes). For this analysis, participants who do not have intended PCC use data collected will be excluded.

Sensitivity analysis 2: The same analysis for the primary endpoint described in Section 5.3.2 on the PPS.

Sensitivity analysis 3: The same analysis for the primary endpoint described in Section 5.3.2 on the ITT Set, excluding participants with nonevaluable hemostatic status due to administrative reasons.

Sensitivity analysis 4: To evaluate the impact of the missing hemostatic status due to administrative reasons, 3 statistical methods for missing data imputation will be applied on the ITT Set as follows:

Page 20 of 52 Alexion Confidential **Worst-case scenario imputation**. In this case, missing hemostatic status in the andexanet group will be imputed as poor/none, whereas missing status in the UC group will be imputed as excellent/good. The same method used in the primary analysis described in Section 5.3.1 will be used to compare andexanet and UC. This imputation represents the worst possible case for missing hemostatic status; if the statistical comparison reaches significance (p < 0.05), the following imputation methods will not be performed.

Jump-to-control imputation. This approach imputes missing hemostatic status using only data from the UC group. For a given participant with missing status, his/her status will be generated based on the probability of effective hemostasis in the UC group estimated with available data, regardless of the treatment group this participant is randomized to.

Tipping point. In this case, missing hemostatic status will be imputed over a series of scenarios to evaluate at what point the significance in andexanet and UC comparison will be overturned.

A logistic regression model will be first estimated for the effective hemostasis, with treatment group and time from symptom onset to the baseline imaging scan in the model. Then, a shift parameter δ will be applied to the log odds ratio in the logistic regression model to impute the missing data.

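### The per-protocol dose-completeness rule covers andexanet only and makes no exception for clinical reasons, so it can drop early failures from that arm in sensitivity analysis 2

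*SAP*

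**What the plan says.** SAP Section 4 refers to SAP 6.1 for the detailed PPS rules, so 6.1 is the operative text. Its list is introduced as a subset of major protocol deviations. Under andexanet administration, below the line "Missing dose or Treatment administered incorrectly", it gives four cut-offs:

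- "Low and examet bolus dose if < 360mg administered"
- "High and exanet bolus dose if < 720mg administered"
- "Low and exanet infusion dose if < 432mg administered"
- "High and exanet infusion dose if < 864mg administered"

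The same block excludes participants whose infusion began more than 15 minutes after the bolus ended. None of these items refers to the reason. Other PPS items do carry exceptions, for example where the core-laboratory volume is within limits or the EAC can still determine an outcome.

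SAP 5.3.3 defines sensitivity analysis 2 as "The same analysis for the primary endpoint described in Section 5.3.2 on the PPS".

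Protocol 4.4 foresees early discontinuation of andexanet. The reason it lists is "Any intolerable AE that cannot be ameliorated by appropriate medical intervention"; patients who stop remain in the study, and the reasons are recorded. Protocol 7.5 also allows slowing the infusion, or "temporary interruption of the dose followed by re-starting the infusion at a slower infusion rate".

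Usual care may consist of no treatment (SAP 1.2), and the PPS has no dose or completeness rule for it. The PPS exclusion aimed specifically at usual care is for andexanet given before 12 hours.

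**The concern.** Receiving the full dose is a post-randomization event that can depend on how the patient is doing. A patient who dies, deteriorates or goes to emergency surgery during the infusion is a likely endpoint failure and is also likely to fall below 90% of the planned dose. A patient who deteriorates before the bolus receives 0 mg, which is below every cut-off. Applied literally, the rule drops these patients if they were randomized to andexanet. With the same course under usual care they stay in the PPS as poor/none.

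This sits badly with the SAP's own principle. SAP Table 3 and SAP 6.1 count cases that are non-evaluable for clinical reasons as poor/none. For missing or confounded NIHSS and imaging, the PPS drops only cases that the EAC calls non-evaluable for administrative reasons. At stake is a robustness analysis that could appear to support a benefit partly because failures had left one arm.

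**Working it through.** **Cut-offs against plan** (planned doses from SAP 1.2): 360/400 = 720/800 = 432/480 = 864/960 = 0.90.

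**When the rule bites** (target rates from Protocol Table 3):
- Low dose: 400/30 = 13.3 min of bolus, plus 432/4 = 108 min of infusion, gives about 121 min.
- High dose: 800/30 = 26.7 min, plus 864/8 = 108 min, gives about 135 min.

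At target rates, any stop before roughly 2 to 2.25 hours from bolus start leads to exclusion.

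**Base rates.** SAP Section 3 assumes 70% (usual care) and 80% (andexanet), with 450 per group and about 90% power. With Lan-DeMets Pocock-type spending at half information, the plan's levels of 0.0310 and 0.0277 reproduce. Power is 90.9% without dropout and 89.4% at 5% dropout. No stated figure is disputed; these rates are only the starting point.

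**Effect of the exclusion.** Let p be the true andexanet rate, f the share of the arm removed, and s the share of the removed who are failures. Then

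PPS rate = [p − f(1 − s)] / (1 − f).

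The documents give neither f nor s; both are assumptions. With no true effect (p = 70%, usual care 70%):

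| f | s = 100% | s = 60% | s = 30% (arm's own rate) |
|---|---|---|---|
| 3% | 0.700/0.97 = 72.2% (+2.2) | 0.688/0.97 = 70.9% (+0.9) | 0.679/0.97 = 70.0% (0) |
| 5% | 0.700/0.95 = 73.7% (+3.7) | 0.680/0.95 = 71.6% (+1.6) | 0.665/0.95 = 70.0% (0) |

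The chance of a PPS result favoring andexanet at two-sided 0.05 (unstratified z-test, 450 per arm before exclusion) is 2.5% with no exclusion. It becomes 10.6% (f = 3%) or 22.7% (f = 5%) at s = 100%, and 4.9% or 7.4% at s = 60%.

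At the planned 80% vs 70% with s = 100%, the 10-point difference reads 82.5 − 70 = 12.5 points (f = 3%) or 84.2 − 70 = 14.2 points (f = 5%).

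**Counterweight from usual care.** Protocol Appendix B rates andexanet started between 3 and 12 hours as poor/none, and the PPS removes such usual-care patients. If 1% of that arm were removed and all were failures, its rate would be 0.70/0.99 = 70.7%. Against 72.2% for andexanet (f = 3%, s = 100%), the net shift is 1.5 points instead of 2.2.

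**The case against.** The strongest reply is that the list is confined to major protocol deviations and that its heading and labels suggest administration errors. If a stop allowed by Protocol 4.4 is not a deviation, the patient arguably stays in the PPS. That reading is possible. The SAP does not state it: it classes any amount below the cut-off as a wrong dose and writes exceptions for other items but not this one. SAP 6.2.1 refers to a protocol deviation review plan, which might settle the matter but is not among these documents.

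Several limits do stand:

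- A reader might infer that the SAP orders removal for any reason, including deterioration or death. It is silent on reason; removal follows only from a literal reading.
- A reader might infer that the rule deletes failures as such, and only from one arm. It removes under-dosed patients whatever their outcome, and the usual-care rule on andexanet before 12 hours also removes patients rated poor/none.
- Under Protocol 8.1.1, hematoma expansion and related deterioration in the first 12 hours are generally not AEs. A stop for an AE is therefore often a different event from an endpoint failure.
- The cut-offs are in mg, not minutes. An infusion slowed or restarted under Protocol 7.5 and then completed is not excluded by them.
- A completeness rule is conventional in a per-protocol set, and usual care that may be no treatment cannot have an equivalent one.
- PPS counts by arm, set-status listings and deviations by arm are already planned (SAP 5.2.1, 6.2.1), so unequal exclusion would be partly visible.

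**Conclusion.** The point holds as a gap in a planned sensitivity analysis. The dose rule applies to andexanet only, has no carve-out for clinical reasons, and can remove early failures from that arm. The direction is probably, not certainly, toward andexanet.

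The size rests on two unknowns, the share short-dosed for clinical reasons and their failure share. With no true effect and 3% to 5% removed, the range runs from no shift to 3.7 points. The 14.2-point figure needs 5% removed, every one a failure, and no offsetting removals from usual care; it is an upper illustration, not an expectation.

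A reader might infer that the trial's main conclusion is at risk. The documents do not support that: the primary analysis uses the ITT Set (SAP 5.3), both kinds of non-evaluable case count there as poor/none, and no success criterion uses the PPS.

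**What to change.** In SAP 6.1:

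1. Limit the under-dose and infusion-gap exclusions to preparation or administration errors.
2. Add a sentence such as: *Participants whose andexanet was not completed for a clinical reason (AE, deterioration, surgery, death) remain in the PPS with their EAC or algorithm outcome.* Use the discontinuation reasons recorded under Protocol 4.4.
3. Tabulate PPS exclusions by arm, reason and outcome.

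No parallel change is needed for usual-care patients given andexanet. Protocol 7.4 does not allow that dosing, so it is a genuine deviation, and excluding it is a normal per-protocol choice.

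The cost is SAP wording, one derivation and one table; patient management is untouched. Protocol 4.4 promises reasons for discontinuations only, so check whether the CRF also gives reasons for reductions and for doses never started. The downside is small: the PPS would contain a few incompletely dosed patients and might look slightly less favorable.
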